Note: Patients with a suspected case of HZ who have pain persisting longer than 6 months should continue in HZ follow-up until the pain resolves or the study ends.

Note: Deviations from the 6-month suspected HZ case follow-up period as scheduled per protocol because of medical or logistical reasons require consultation between the investigator and the Sponsor and written documentation of the collaborative decision.

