### 3.2.17.3 Suspected HZ Case Follow-Up (Cases With HZ and HZ-like Rash)

All patients who experience rash or other symptoms that could be due to a suspected case of HZ should be seen by a medically qualified investigator, (defined as a physician, or in accordance with local regulations, a nurse practitioner or physician assistant) as soon as possible, preferably within 24 to 72 hours of rash onset. The medically qualified investigator's description and assessment of the rash, associated complications and complaints, and the patient's history of exposure to varicella and/or HZ should be recorded on the appropriate eCRFs. In addition, the patient should have a skin lesion swab and blood sample collected for VZV identification by PCR at the initial rash visit. The patient should be evaluated by a medically qualified investigator every 3-5 days until no new skin lesions appear. If the rash is a suspected case of HZ, the patient should undergo all procedures and follow-up visits required for suspected HZ cases.

All patients with suspected cases of HZ will be entered into a 6-month suspected HZ case follow-up. Deviations from the 6-month suspected HZ case follow-up period due to medical or logistical reasons require consultation between the investigator and the Sponsor and written documentation of the collaborative decision. If a patient has multiple suspected cases of HZ, each case must go through the 6-month follow-up procedures. If a patient with a suspected case of HZ has pain persisting longer than 6 months, he/she should continue in HZ follow-up until the pain resolves or the study ends.

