- The severity-by-duration of HZ pain (defined as the average area under the “worst pain in the last 24 hours” versus time curve) from the first day of HZ onset through 6 months after HZ onset.
- The duration of pain (defined as number of days from rash onset to the first visit when pain score on the ZBPI became persistently < 3).
- The numbers of lesions, number of dermatomes and extent of rash (defined as the maximum area of the HZ rash at each HZ follow-up visit).
- The impact of HZ on ADL, as measured by the score-by-duration of activity-of-daily-interference (ADLI) (defined as the average area under ADLI versus time curve) from the first day of HZ onset through 6 months after HZ onset. ADLI is a single combined score calculated by averaging 7 separate items (regarding general activity, mood, walking ability, normal work, relations with others, sleep, and enjoyment of life) collected in the ZBPI at each HZ follow-up visit.
- The impact of HZ on general health status, as measured by the score-by-duration in the EuroQoL from the first day of HZ onset through 6 months after HZ.
- HZ-related non-protocol-mandated HCU and work and productivity loss. The analyses will be covered in a separate internal SAP, prepared by the Health Economist of the study.

Of note, the exploratory efficacy analyses will be evaluated for the HM and STM populations separately.

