## **3.5.5 Statistical Methods**

### **3.5.5.1 Analysis of Vaccine Efficacy**

Table 3-2 summarizes the key efficacy analyses to be performed. The details are given in the following subsections.

Table 3-2

Summary of Key Efficacy Analyses Performed

Analysis	Method	Patient population
Primary		
HZ incidence - $VE_{HZ}$	Cox proportional hazards regression model with Efron's method of tie handling	MITT
Secondary		
(1) Incidence of moderate to severe HZ-associated pain	Cox proportional hazards regression model with Efron's method of tie handling	MITT
(2) A composite efficacy endpoint of the incidence of HZ complications during the study	Same as above	MITT
(3) Incidence of PHN	Same as above	MITT
Supportive		
HZ incidence - Vaccine efficacy	Cox proportional hazards regression model with Efron's method of tie handling	PP
Durability of efficacy	Kaplan-Meier method Piecewise exponential model	MITT MITT
Exploratory endpoints - Severity-by-duration of HZ pain Duration of pain Score-by-duration of ADLI Score-by-duration of general health status score (EuroQoL) Impact of HCU and Work and Productivity Loss HZ incidence	ANCOVA Summaries ANCOVA ANCOVA Poisson regression with generalized estimating equations Summaries by age categories and HM population	MITT

It should be noted that if a given patient develops two or more episodes of confirmed HZ, only the first episode will be used in the vaccine efficacy analyses. The patients with multiple episodes of HZ will be listed. Exploratory analysis of multiple episodes of HZ (such as the Wei, Lin and Weissfeld method [51]) may also be performed if a sizable proportion (e.g., >10%) of HZ patients develop multiple episodes.

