### **3.5.5.1.3 Analysis of Vaccine Efficacy on Exploratory Endpoints**

The following exploratory efficacy analyses will be conducted for the STM and HM populations separately.

To evaluate the vaccine effect on the severity of HZ pain among HZ cases, the severity-by-duration of HZ pain (calculated as the area under the “worst pain in the last 24 hours” versus time curve) will be summarized by vaccination group on a MITT population. To compare the mean severity-by-duration measure of HZ pain among patients who develop HZ between the two vaccination groups, an analysis of covariance (ANCOVA) model adjusting for similar covariates as for the primary efficacy analysis will be used to get the point estimate and a bootstrap method will be used to obtain 95% CI of HZ severity-by-duration scores difference between the vaccination groups. Additional exploratory analysis may include the use of antiviral drug initiated within 72 hours of HZ rash onset (Yes versus No) as an additional covariate.

In addition, the mean and median duration of HZ pain (time from rash onset to the first visit when pain score became persistently < 3) will be provided by vaccination group. The mean HZ pain score, the numbers of lesions, dermatomes and extent of rash (defined as the maximum area of the HZ rash at each HZ follow-up visit), the mean ADLI score and the mean EuroQoL score will be summarized by vaccination group. ANCOVA models will also be used to compare these mean scores between the two vaccination groups at each HZ follow-up visit. In addition, the score-by-duration of ADLI and score-by-duration of general health status score in EuroQoL over 6 months post-HZ onset (calculated by area under the ADLI curve and general health status score curve, respectively) will be summarized by vaccination group and compared by ANCOVA model.

Poisson regression with generalized estimating equations will be used to evaluate the effect of the vaccine on the rates of non-protocol mandated health care utilization and work loss. If the counts of health care contacts in each treatment group are less than 10, then an exact binomial method will be used to calculate the CIs rather than generalized estimating equations.

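### Pain duration has no value until pain resolves, and the plan has no rule for unresolved cases, so its raw mean is biased low by an unknown amount

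*Combined protocol and SAP*

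**What the plan says.** Section 3.5.3.1 defines pain duration as the "number of days from rash onset to the first visit when pain score on the ZBPI became persistently < 3". Section 3.5.5.1.3 repeats this ("time from rash onset to the first visit when pain score became persistently < 3") and plans "the mean and median duration of HZ pain" by vaccination group, for STM and HM separately. In Table 3-2 the methods for the first four exploratory endpoints read "ANCOVA Summaries ANCOVA ANCOVA". The second entry lines up with duration of pain, so descriptive summaries are the only method assigned to it.

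On follow-up, section 3.2.17.3 says: "All patients with suspected cases of HZ will be entered into a 6-month suspected HZ case follow-up". Section 1.8 adds that patients "who have pain persisting longer than 6 months should continue in HZ follow-up until the pain resolves or the study ends". At close-out, patients already in suspected-HZ follow-up complete their 6-month period (1.7 footnote, 2.4.1, 3.2.19); nothing longer is assured.

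Section 3.5 states that no separate SAP will be issued. The one separate internal plan mentioned (3.5.3.1) covers health care use and work loss.

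**The concern.** The definition gives a number only to patients who reach resolution. Someone who dies, is lost, or still has pain of 3 or more at study end has a right-censored duration, and these patients tend to be the ones with the longest pain. A raw mean or median needs a number from everyone or a reason to leave someone out, and the plan supplies neither. Whoever programs the table must choose between dropping these patients and treating last contact as the end of pain.

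Exploratory objective 9 concerns the effect of V212 on the severity and duration of HZ pain. At stake is whether the reported durations describe all HZ cases or only those whose pain resolved under observation.

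**Working it through.** **1. Is there a rule elsewhere?** Censoring is stated for HZ (3.5.5.1.1) and for PHN (3.5.5.1.2). The severity-by-duration score has a fixed 6-month window (3.5.3.1). Pain duration has neither a censoring rule nor a time horizon.

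**2. Will unresolved cases occur?** The documents give no unresolved share, but some such cases are foreseeable. Required life expectancy is at least 12 months (2.2), 30% total loss to follow-up is assumed (3.5.7.1), and death and loss are listed as final dispositions (3.2.19). The HM arm, which is also analysed for this endpoint, began close-out on 19-Nov-2014 (1.4).

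**3. How many cases are there?** The plan gives no expected value or precision for pain duration, so there is no figure of its own to reproduce. The case count behind it does check. An exact conditional binomial with 90 cases, null vaccine share 0.75/1.75, alternative share 0.35/1.35 and one-sided 0.0125 succeeds with at most 27 vaccine cases. Its power is 84.2%, as in Table 3-3. At VE 65% the expected split is 90 × 0.35/1.35 = 23 vaccine and 67 placebo cases. Pain at or beyond 90 days, at the 8.6% cited in 3.1.1.2, would be 90 × 0.086 = about 8 cases (2 vaccine, 6 placebo).

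**4. Size of the bias in one group.** These durations and loss rates are assumptions. Duration is log-normal with median m and a share f at 90 days or more, so σ = (ln 90 − ln m)/z(1−f) and the true mean is m·exp(σ²/2). For m = 30, f = 0.086: σ = 1.099/1.366 = 0.804 and the mean is 41.5 days. For m = 30, f = 0.20: σ = 1.099/0.842 = 1.305 and the mean is 70.3 days. Loss is 20% per year. Simulated means, with the shortfall against the true mean in parentheses:

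| m | f | Observation | Unresolved | True mean | Dropped | Set to last contact |
|---|---|---|---|---|---|---|
| 30 | 8.6% | to resolution | 2.5% | 41.5 | 40.6 (2%) | 40.5 (2%) |
| 20 | 8.6% | to resolution | 2.2% | 36.6 | 34.9 (5%) | 35.3 (4%) |
| 30 | 20% | to resolution | 3.9% | 70.3 | 61.1 (13%) | 63.9 (9%) |
| 20 | 20% | to resolution | 4.6% | 99.0 | 65.3 (34%) | 75.1 (24%) |
| 30 | 20% | also stops at 182 days | 10.6% | 70.3 | 39.7 (44%) | 50.8 (28%) |

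In the first row the median of 30.0 becomes 29.6 (dropped) or 29.5 (last contact). In the last row it becomes 25.5 (dropped) or 29.1 (last contact). The last row is an upper illustration, because the protocol does not stop at 182 days for persisting pain except where the study ends. At f = 42%, the top of the published range in 3.1.1.2, the assumed distribution has no usable mean, so that case is left out.

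**5. Direction between groups.** Assume resolved cases average 30 days and long cases 300 days.

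- *Long cases 5% vaccine, 15% placebo, all unresolved.* True means: 0.95×30 + 0.05×300 = 43.5 and 0.85×30 + 0.15×300 = 70.5, a difference of 27 days. Dropping gives 30 and 30, a difference of 0. Cutting at 182 days gives 37.6 and 52.8, a difference of 15.2.
- *8.6% in both groups, all unresolved.* Both true means are 0.914×30 + 0.086×300 = 53.2. The difference is zero before and after either shortcut.
- *15% in both groups, but only the vaccine group's long cases are lost before resolution.* Both true means are 70.5. Dropping gives 30 against 70.5, a spurious difference of 40.5 days.

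So the contrast can shrink, stay the same or be exaggerated.

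**The case against.** The best case for the plan is that little is lost. Every suspected case gets 6 months of follow-up, persistent pain is followed further, and cases open at close-out still complete 6 months. Study end alone therefore cannot cut a case before about 6 months; only death or loss can. If few remain unresolved, the mean moves by a few percent, and a median with unresolved cases kept at last contact hardly moves. Objective 9 is also served by the 6-month severity-by-duration comparison (ANCOVA with a bootstrap interval), while PHN at several cut-offs describes persistence. Neither needs a resolution date. The duration summary carries no test and no decision.

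All of that stands, and it limits the point. It does not supply a rule for the patients without a value.

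A reader might go further and treat the 8.6% PHN share as the unresolved share. With assumed durations of 30 days (resolved) and 200 to 300 days (unresolved), the true mean would be 44.6 to 53.2 days, and a dropped-case mean of 30 would be 33% to 44% low. Section 3.1.1.2 does not support that. The 8.6% is pain persisting or appearing at or beyond 90 days, and many such cases may resolve under observation.

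A reader might also infer that the vaccine effect on duration is bound to be understated. That needs the unresolved share and the pattern of death and loss by group, and the documents give none of these.

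**Conclusion.** The point holds as a gap in an exploratory analysis. A right-censored time is summarised by a raw mean and median with no rule for unresolved cases. Either available shortcut biases the mean downward whenever such cases exist; the median is exposed mainly if they are dropped. For deaths, even the target value needs a convention that the plan does not state.

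The size cannot be fixed from the documents. In the illustration with a 30-day median it runs from about 2% low with 2.5% unresolved to 28% to 44% low with 10.6% unresolved. A heavier assumed tail gives larger errors at smaller shares. With about 23 vaccine and 67 placebo cases, a few patients can move a group mean. Attenuation of the vaccine effect is possible but not established. No primary or secondary conclusion is touched.

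**What to change.** In 3.5.5.1.3 and Table 3-2, replace the raw summaries with an analysis of time to pain resolution, censored at the last pain assessment. Report by group:

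- the Kaplan-Meier median;
- the restricted mean to 182 days, which matches the 6 months of follow-up assured for every case;
- the number unresolved at last assessment, split by death, loss and study end.

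State how deaths are handled, for example censored, with a sensitivity analysis that treats death as a competing event. This matters because uninformative censoring by death is doubtful in patients with cancer. Raw durations beyond 6 months can still be listed, so the extended follow-up data are not lost.

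This is a cheap improvement: a few sentences of plan wording and one more standard table, with no new data collection. The downside is that the mean is restricted to 6 months.

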## 1.8 STUDY FLOW CHART FOR PATIENTS WITH SUSPECTED HZ

	Onset of rash or other symptoms of HZ	First Evaluation †	Every 3 to 5 days until no new lesions appear/acute HZ symptom(s) improve	1 month post-symptom onset	2 months post-symptom onset	3 months post-symptom onset	4 months post-symptom onset	5 months post-symptom onset	6 months post-symptom onset
Visit window permitted (days) ‡	N/A	N/A	N/A	(+/-5 days)	(+/-5 days)	(+/-5 days)	(+/-5 days)	(+/-5 days)	(+/-5 days)
Patient calls site	X								
Perform assessment of HZ rash, acute HZ-related symptom(s) and HZ-related complications §		X	X						
Collect lesion sample for PCR (for patients with an HZ-like RASH) 		X							
Collect blood sample for PCR (for all patients with suspected HZ) ¶		X							
Assess for exposure to varicella or HZ #		X							
Perform ZBPI assessment ††		X	X	X	X	X	X	X	X
Perform EuroQol-EQ5D assessment †‡		X	X	X	X	X	X	X	X
Perform HCU assessment †§		X	X	X	X	X	X	X	X
Perform WPQ assessment †  		X	X	X	X	X	X	X	X

† All patients who experience rash or other symptoms that could be due to a suspected case of HZ should be seen by a medically qualified investigator (defined as a physician, or in accordance with local regulations, a nurse practitioner or physician assistant) as soon as possible, preferably within 24 to 72 hours of rash onset. Antiviral therapy should be started and diagnostic procedures should be performed as soon as possible after HZ symptom onset. Report all concomitant medications (i.e., antiviral treatment, pain medications) administered as a result of a suspected case of HZ for the duration of the study.

‡ Study procedures may be performed up to 5 days prior or 5 days following the scheduled visit day. Deviations from the permitted visit windows (i.e., if the patient will not be able to complete visit as scheduled per protocol because of medical or logistical reasons) require consultation between the investigator and the Sponsor and written documentation of the collaborative decision on patient management.

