#### **2.1.4 Exploratory Objectives**

1. To assess the safety and tolerability of V212 when administered to adults with HM.
2. To assess the impact of V212 on the development of HZ in adults with HM.
3. To assess the impact of V212 on the development of moderate to severe HZ-associated pain at any time from HZ onset through the end of the 6 month HZ follow-up period. Moderate to severe HZ-associated pain is defined as 2 or more occurrences of a score of 3 or greater (0-to-10 scale) on the Zoster Brief Pain Inventory (ZBPI) in adults with HM.

4. To assess the impact of V212 on the development of HZ complications defined as the occurrence of any of the following during the study: hospitalization or prolongation of hospitalization due to HZ, disseminated HZ (including disseminated HZ rash or VZV viremia), visceral HZ, ophthalmic HZ, neurological impairment due to HZ, or administration of intravenous acyclovir therapy for treatment of HZ in adults with HM.
5. To assess the impact of V212 on the development of PHN. PHN is defined as a worst pain score (in the previous 24 hours) of 3 or greater (0-to-10 scale) on the ZBPI, that persists or appears greater than or equal to 90 days after the onset of HZ rash in adults with HM.
6. To assess the immunogenicity of V212 in adults with STM or HM.
7. To describe the impact of HZ on activities of daily living (ADL) and quality of life (QoL), and to assess the impact of V212 on interference with ADL and QoL in study patients who develop HZ.
8. To describe HZ-related non-protocol-mandated health care resource utilization (HCRU), and assess the impact of V212 on HZ-related non-protocol-mandated HCRU, and work and productivity loss (WPQ).
9. To assess the impact of V212 on the severity and duration of HZ-related pain.
10. To assess the impact of V212 on the severity of HZ rash including the extent of rash, number of skin lesions present, and number of dermatomes involved.
11. To assess the association of immunogenicity at postvaccination with the risk of HZ in adults with STM or HM.

The exploratory objectives (1)-(5) will be evaluated for HM only; objectives(6)-(10) will be evaluated for STM and HM separately and (11) will be evaluated in both combined STM and HM populations and individual subpopulation.

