### **Visits During Rash Progression**

- a) Perform a full physical exam every 3-5 days until no new skin lesions appear. Clinical findings as well as relevant laboratory results must be reported. These findings will include descriptions of the evaluation of dermatomal involvement, and the morphologic characteristics of the rash, including new vesicle formation, number of lesions, and the extent of rash, and any HZ-associated complications. Record all medications administered for HZ treatment or HZ symptom relief.
- b) Repeat steps e through h as above.

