### **Visits Following Cessation of New Lesion Formation**

- a) Conduct monthly evaluations for 6 months from HZ rash onset. Assessments may be obtained by telephone or at a study visit. All information should be reported.
- b) Repeat steps e through h as above.

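### By-visit comparison of rash severity after the first evaluation covers only cases still under acute follow-up, so a vaccine effect on rash can be attenuated; one maximum per episode would avoid this

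*Combined protocol and SAP*

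**What the plan says.** Exploratory objective 10 (Section 2.1.4) concerns the effect of V212 on "severity of HZ rash including the extent of rash, number of skin lesions present, and number of dermatomes involved".

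Section 3.5.5.1.3 lists the measures to be summarized by group: mean pain score, "the numbers of lesions, dermatomes and extent of rash (defined as the maximum area of the HZ rash at each HZ follow-up visit"), mean ADLI score and mean EuroQoL score. The next sentence reads: "ANCOVA models will also be used to compare these mean scores between the two vaccination groups at each HZ follow-up visit". Section 3.5.3.1 also defines rash extent per visit.

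The flow chart in Section 1.8 marks rash assessment in two columns only: the first evaluation, and the column headed "Every 3 to 5 days until no new lesions appear/acute HZ symptom(s) improve". No monthly column is marked. Section 3.2.17.3 has the same rule for visits during rash progression: "Perform a full physical exam every 3-5 days until no new skin lesions appear". For the monthly contacts after that, it says "Assessments may be obtained by telephone or at a study visit" and "Repeat steps e through h as above". Those steps are the ZBPI, the health care utilization and work productivity interviews, and the EuroQoL. None of them assesses the rash.

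The plan names no per-episode rash summary and gives no rule for cases whose acute visits have ended. Section 3.5.5.1.2 warns that comparisons are not protected by randomization, but only for PHN among HZ cases.

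**The concern.** Whether a patient has a rash value at the second, third or fourth acute visit depends on how long lesions keep forming, which is closely tied to the severity that objective 10 asks about. If the vaccine makes episodes milder partly by making them shorter, fewer vaccine cases than placebo cases remain at each later visit, and those that remain are the longer-lasting ones. The contrast then compares a more strongly selected vaccine subset with a less strongly selected placebo subset.

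The first evaluation has no such selection, but it is meant to fall preferably within 24 to 72 hours of rash onset, when the rash may not yet be fully developed. A real reduction in rash severity could therefore look smaller than it is at every visit compared. Pain, ADLI and EuroQoL scores are also collected at the repeat acute visits, and their by-visit contrasts there share the selection.

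**Working it through.** **Cases available.** The plan gives no figure for the rash analysis. Its power figure supplies the number of STM cases that can enter. By the exact conditional binomial with 90 cases, the vaccine share is 0.75/1.75 = 0.4286 at the 25% null bound and 0.35/1.35 = 0.2593 at VE 65%. At most 27 vaccine cases meets one-sided 0.0125 (probability 0.0083 under the null; 28 would give 0.0149). Power is P(X ≤ 27 | 0.2593) = 0.842, the stated 84.2%. Expected cases are 90 × 0.2593 ≈ 23 vaccine and 67 placebo, and fewer with a rash.

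**Illustrative model.** All severity and attendance inputs are assumptions, because the documents give none.
- Lesion-forming time: L = mean × Gamma(shape 2, scale 0.5); placebo mean 6 days.
- Peak count: 100 × I × (L/6) × lognormal(0, 0.5), where I is relative intensity.
- Count at day t: peak × min(1, t/L).
- Visits: first on a day uniform between 1 and 3, then every 4 days. A patient has a next visit if L exceeds the day of the previous one, so the visit that finds no new lesions is included.

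Mean peak on placebo is 100 × exp(0.125) = 113.3. Each vaccine scenario has a mean peak of about 75.5, for example 113.3 × 4/6 or 113.3 × (5/6) × 0.8. The true reduction is therefore 33% in all three. Simulated with 2,000,000 cases per arm:

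| Assumed vaccine mechanism | Visit 1 | Visit 2 | Visit 3 | Visit 4 | Still assessed at visit 3, vaccine v placebo |
|---|---|---|---|---|---|
| Shorter lesion formation only (4 v 6 days) | 6% | 12% | 7% | 5% | 20% v 41% |
| Both (5 v 6 days, intensity × 0.8) | 22% | 24% | 22% | 22% | 31% v 41% |
| Lower intensity only (× 2/3) | 33% | 33% | 33% | 33% | 41% v 41% |

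The arithmetic for the first row, from the simulated means, is 1 − 33.3/35.4 = 0.06, 1 − 80.6/92.0 = 0.12, 1 − 149.2/161.0 = 0.07 and 1 − 222.9/234.3 = 0.05. The 6% at visit 1 reflects an incompletely developed rash, not selection. In that row about 0.20 × 23 ≈ 5 vaccine cases and 0.41 × 67 ≈ 27 placebo cases have a visit-3 value.

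**Second model, selection only.** Each case has a fixed severity, 0.5 SD lower on vaccine, and about 55% of placebo cases need a further acute visit. The share of the true difference seen at visits 1 / 2 / 3 / 5 is:
- stopping unrelated to severity: 100 / 100 / 101 / 99%
- weakly related: 100 / 87 / 78 / 68%
- moderately related: 100 / 70 / 58 / 46%
- strongly related: 100 / 54 / 43 / 35%

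If the vaccine also shortens the lesion phase by more than its severity effect implies, the later difference can fall to about zero or reverse.

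**Per-episode value.** In the first model, the count at each patient's last acute visit averages 113.3 on placebo and 75.5 on vaccine, equal to the true peaks. The data collected are enough to recover the full 33%.

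**The case against.** Several points on the other side stand.

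- **The ANCOVA may not cover rash.** Only pain, ADLI and EuroQoL are called mean scores in the list, and Table 3-2 assigns ANCOVA to three score-by-duration measures and lists no rash measure. A descriptive-only reading is at least as natural. But objective 10 would then have no specified between-group comparison, so the wording needs settling either way.
- **A reader might infer that the plan masks a vaccine effect on rash.** The documents do not support this. The first evaluation is free of the selection, and the loss at later visits depends on how severity and duration are linked, on which the documents are silent.
- **A reader might infer that no visit measures the episode.** That is wrong: acute visits run until new lesions stop, so the last one records the completed rash.
- **A reader might cite the 3-dose proof-of-concept study as evidence that the vaccine shortens HZ.** Section 3.1.2.2 reports lower severity for that regimen and says nothing about duration.
- **Pain, ADLI and EuroQoL are largely safe.** They are collected monthly for 6 months from every suspected case, and their score-by-duration analyses span the whole episode.
- **The stakes are small.** Objective 10 is exploratory, with no hypothesis or multiplicity control. Section 3.5 allows exploratory analyses to be changed if this is explained in the study report.

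**Conclusion.** The point holds in a limited form. If rash measures enter the by-visit ANCOVA, contrasts after the first evaluation are conditioned on continuing lesion formation, and the first evaluation may be too early to show the full rash. A vaccine effect on rash severity can then be attenuated. With a true 33% reduction and the assumed inputs above, the loss runs from none (vaccine lowers intensity only) to most of the effect (vaccine shortens lesion formation only, 5-12% seen). The size rests wholly on those assumptions, and nothing in the documents favours one mechanism.

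Pain, ADLI and EuroQoL are affected only at the repeat acute visits. Their monthly contrasts and 6-month score-by-duration analyses are not affected by this stopping rule. This is a worthwhile minor improvement to an exploratory analysis, with no bearing on the primary or secondary efficacy results.

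**What to change.** In Sections 3.5.3.1 and 3.5.5.1.3:

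1. State whether lesion number, dermatomes and rash extent enter the ANCOVA.
2. For objective 10, compare one value per confirmed HZ case with rash: the maximum lesion number, maximum dermatome number and maximum rash area over the whole acute phase.
3. Limit by-visit ANCOVA of pain, ADLI and EuroQoL to the contacts every case is scheduled to have: the first evaluation and months 1 to 6.
4. Show values at repeat acute visits descriptively by group, with the number still under acute follow-up.
5. Extend the existing caveat: any comparison among HZ cases, including the per-episode maximum, is not protected by randomization.

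The cost is wording and three derived variables from data already collected; the visit schedule does not change. The downside is that acute-visit comparisons become descriptive.
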